# 1.3b Secondary Aims/Hypotheses un-related to the primary hypothesis include the following:

- a) To assess whether antihypertensive treatment of mild CHTN during pregnancy (compared to standard care) increases post-pregnancy adherence to recommended therapy.
- b) To assess the impact of postpartum treatment recommendations on maternal outcomes
- c) To investigate the optimal gestational age to deliver women with CHTN in order to minimize maternal and perinatal complications. We will apply survival analysis methods to the trial population.
- d) To collect and store biospecimens including maternal and cord blood for future biological and biophysical studies to understand the effects of antihypertensive therapy in pregnant women with mild CHTN.
- e) To compare outcomes based on standardized pragmatic clinic BP vs. standardized automated clinic BP measures
- f) To assess whether the effect of therapy on SGA differs by whether current national standard nomogram vs. individualized nomogram for birth weight is utilized.
- g) To plan for a long-term follow-up study to evaluate the impact of treatment of mild-moderate chronic hypertension on long-term maternal and child outcomes.

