#### 2.7.2 INNOVATIONS

The study will answer critical questions about the impact of treating CHTN in pregnancy and lead to innovations in obstetric care worldwide. The assembled cohort of pregnant women with CHTN will create the opportunity for a follow-up study to further our knowledge of the long-term impact of CHTN in pregnancy.

- a) Pregnancy care: By delineating the benefits and possible harms of antihypertensive therapy in pregnancy, the study will define the optimal management of CHTN in pregnancy. By using pragmatic clinic BPs and also collecting automated standardized BPs using an automated oscillometric device, we will be able to evaluate the benefits and harms of pragmatic vs. standardized automated BP. Furthermore, the optimal timing of delivery is controversial some experts suggest no sooner than 39 weeks while others suggest 38 weeks or earlier. Therefore, relating adverse maternal and perinatal outcomes to gestational age at delivery will help define the optimal window for delivery. The study will also quantify the risks of maternal death and cardiovascular complications in pregnant women with CHTN. Ultimately this knowledge will lead to improved health outcomes for pregnant women with CHTN and their infants. Our findings could impact as many as 260,000 women with CHTN (and their infants) annually in the US (given 4.3 million births) and millions more worldwide.
- b) Post-pregnancy care: If antihypertensive therapy of CHTN during pregnancy is shown to prevent adverse outcomes, a recommendation to treat all pregnant women with CHTN, regardless of severity, would resolve the conflict in treatment recommendations for pregnant women compared to the general hypertensive population. This may positively impact post-pregnancy treatment adherence, improve rates of BP control among reproductive age women, and reduce complications of CHTN in women (a Healthy People 2015 goal). By comparing treatment adherence in the postpartum period between randomized treatment groups, we will determine whether antihypertensive treatment during pregnancy influences postpartum treatment adherence. We will also document treatment status during any prior pregnancies at baseline and will conduct adjusted analyses to investigate how lack of antihypertensive treatment during recurrent pregnancies influences subsequent medication adherence.

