#### 3.3 Design Summary

This study is a multicenter randomized controlled clinical trial of 2404 women with randomization stratified by center (Figure 2). Patients with mild CHTN (based on pragmatic clinic BP measurements <160/105) will be randomized to either treatment with a first-line antihypertensive agent recommended by ACOG (labetalol or nifedipine ER supplied by the study) or other provider preferred medication (not supplied by the study), or no anti-hypertensive treatment. Consistent with the pragmatic design to evaluate the policy of therapy and not a specific medication, rarely, women who have a strong preference for their own established medication (e.g. intolerance of other medications) will be included in the study (and will use their own supply).

For participants in the active treatment group, labetalol dose, nifedipine ER dose or other antihypertensive medication dose will be escalated as needed to achieve target BP (<140/90). Dosing frequency may be increased to tid in order to control BP or to reduce side-effects. If the maximum tolerated oral dose of the first line agent is reached and BP is not at target, 2nd line treatment (labetalol or nifedipine ER) will be initiated to achieve the target BP. After delivery, goal BP will be <140/90 for at least two weeks.

In the comparison group, treatment will not be started if BP remains <160/105; for BP ≥160/105, treatment with a first line agent (labetalol or nifedipine ER) will be initiated and maintained at the lowest dose needed to keep BP <160/105. Goal BP after delivery will follow usual practice at each site.

Analysis will be by intent to treat.

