Once the participant is randomized, the treatment algorithms will be conspicuously placed in her medical record (whether electronic or paper medical record is utilized) such that providers will be aware of treatment plan at all times. The randomly assigned treatment plan will be reviewed with the participant. If a patient is randomized to active treatment, labetalol, nifedipine ER (supplied by the study) or other provider preferred medication (not supplied by the study) to maintain blood pressure <140/90 will be prescribed on the day of randomization. If a patient is randomized to no treatment, any antihypertensive therapy will be stopped on the day of randomization. In both groups, BP measurement will follow recommended guidelines for pregnancy including attention to appropriately sized cuff, period of rest, patient position and repeated measurement to confirm elevation. Baseline data consisting of the pragmatic clinic BP measurements at enrollment, the standardized Omron BP measurements, urine protein results, body mass index, and other prenatal data including baseline BP (first documented BP within 3 months prior to or during pregnancy) will be collected at the randomization visit.

Maternal whole blood, plasma, serum and paxgene specimens will be collected at the randomization and midtrimester (24-30 weeks gestation) visits and stored for future research. Specific collection tubes that will allow for genetic testing and RNA preservation (paxgene) will be used. After delivery, maternal whole blood, plasma and serum will be collected. Cord blood for whole blood, plasma and serum will also be collected at delivery. The placenta will be sent to hospital pathology lab for routine pathology sampling and analysis.

In the active treatment group, a month's supply of the prescribed (supplied) first line medication will be provided to the patient. The medication dose and/or frequency of dosing will be escalated as necessary during subsequent prenatal visits following the specific study treatment algorithm. If the maximum dose of the first

line agent is reached and BP is still uncontrolled, 2nd line therapy (labetalol or nifedipine ER) will be prescribed as indicated to attain BP<140/90. After delivery, study medications or other appropriate BP medication at the provider's discretion will be used to target the goal BP < 140/90 for at least two weeks postpartum.

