In the standard comparison group, participants are randomized to no antihypertensive treatment. They will receive education on the treatment algorithm for the no medication group and will follow the routine obstetric management in place at the clinical site unless the BP increases to a range ≥160/105. A first line agent will be provided to the participants in the comparison group whose BP reaches ≥ 160/105 at the minimum starting dose and only escalated as indicated to keep the BP below 160/105. Dosage frequency may be increased (to tid for labetalol or bid for nifedipine ER) if necessary. After delivery the goal BP for treatment will be according to usual care standards at the site.

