#### 4.5 Participant follow up

Research nurses trained and highly experienced in obstetric and perinatal outcomes abstraction at each center will be responsible for research data abstraction from patient medical records. Outcomes will be ascertained until delivery and maternal/infant discharge. At hospital admission for delivery, maternal blood will be collected at the time of the admission lab work and will be processed for whole blood, plasma and serum samples. At delivery, cord blood will be collected and processed for future studies. These will include a comprehensive assessment of the role and interactions of clinical, biological and biophysical factors (e.g., BP levels, maternal obesity, smoking, glucose intolerance, hyperlipidemia, genes/pharmacogenetics and ultrasound findings) on the occurrence and severity of adverse outcomes including preeclampsia and fetal growth restriction. The placenta will be collected as part of clinical routine and sent to hospital pathology lab for sampling and analysis. Specimens will be frozen and shipped in batches to the UAB Ob/Gyn Diagnostic and Research Lab for storage.

After hospital discharge, participants will be followed up postpartum at 6 (4-12) weeks to ascertain maternal and infant status including readmissions and ER or unscheduled visits. The records of any ER visits or hospitalizations will be obtained for review.

In the active treatment group, the goal blood pressure will remain <140/90 for at least two weeks postpartum. The selection of medication may be based on clinical history, prepregnancy regimen and providers' preference. Participants in the standard care per ACOG (no treatment) arm may be initiated on antihypertensive therapy postpartum per their primary provider; choice of antihypertensive is left to their provider. CHAP will provide study medication when treatment is per protocol (i.e. prescription for labetalol or nifedipine to achieve blood pressure <140/90 for active treatment; prescription for labetalol or nifedipine to achieve blood pressure <160/105 for no treatment arm). The follow-up assessment will include items to assess adherence to antihypertensive therapy since delivery.

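### The postpartum adherence comparison is credited to treatment in pregnancy, but the assigned strategy continues after delivery, so only an effect of the whole strategy can be claimed

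*Combined protocol and SAP*

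**What the plan says.** **The claim.** Protocol section 2.7.2 b says of the post-pregnancy comparison: "By comparing treatment adherence in the postpartum period between randomized treatment groups, we will determine whether antihypertensive treatment during pregnancy influences postpartum treatment adherence". Aim 1.3b a asks whether treating mild chronic hypertension in pregnancy "increases post-pregnancy adherence to recommended therapy". Aim 3.2b d repeats this with a neutral verb.

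**After delivery, active arm.** Section 4.3 says that study or other suitable drugs "will be used to target the goal BP < 140/90 for at least two weeks postpartum". Section 4.5 repeats it: "In the active treatment group, the goal blood pressure will remain <140/90 for at least two weeks postpartum".

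**After delivery, Standard arm.** Section 3.3: "Goal BP after delivery will follow usual practice at each site". Section 4.3: "After delivery the goal BP for treatment will be according to usual care standards at the site". Section 4.5 leaves starting a drug, and the choice of drug, to the woman's provider.

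**Drug supply after delivery.** Section 4.5 lets the study provide labetalol or nifedipine in both arms when treatment follows the protocol. In the active arm that means treatment to below 140/90. In the other arm it means a "prescription for labetalol or nifedipine to achieve blood pressure <160/105 for no treatment arm".

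**The measure.** Protocol sections 4.5 and 4.7.2 (item 8) and SAP section 4.4 (item 9) describe questionnaire items, asked at the 6 (4-12) week visit, on adherence since delivery. The SAP gives no analysis specific to this outcome.

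**The concern.** The named exposure is treatment during pregnancy. The randomized exposure is wider: treatment in pregnancy, then an arm-specific rule on the blood-pressure goal and on drug supply early after birth. That second part bears directly on the outcome, because it affects whether a woman is prescribed an antihypertensive after delivery and whether the study provides it.

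If the arms differ in postpartum adherence, the report as planned would say that being treated in pregnancy changed later behaviour. The same difference could arise, in whole or in part, because one arm was still being managed to a protocol goal during some of the weeks asked about. Section 2.7.2 b links the finding to a recommendation to treat all pregnant women with chronic hypertension. Such a recommendation would not by itself carry a postpartum goal or supplied drug with it.

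**Working it through.** The documents give no rate, effect size or power for postpartum adherence, so there is no plan figure to reproduce. The check is a comparison of texts, plus one piece of arithmetic on the overlap.

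**Step 1. Is the post-delivery rule the same in both arms?**

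| Feature after delivery | Active arm | Standard arm | Source |
|---|---|---|---|
| BP goal | below 140/90 | usual site practice, no protocol number | 3.3, 4.3, 4.5 |
| Stated duration of goal | two weeks or more | none | 3.3, 4.3, 4.5 |
| Drug supplied to reach | below 140/90 | below 160/105 | 4.5 |
| Stated duration of supply rule | none | none | 4.5 |

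It is not the same. On the goal, the contrast is a protocol number against no protocol number. On supply, the two thresholds are explicit and different.

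**Step 2. Does the outcome cover that period?** The recall window starts at delivery and ends at the visit. The two weeks with a fixed goal in the active arm are therefore inside it. Share of window = 2 / (weeks from delivery to visit):

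- 4-week visit: 2/4 = 50%
- 6-week visit: 2/6 = 33%
- 12-week visit: 2/12 = 17%

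The SAP introduction gives follow-up as 6-12 weeks; on that reading the range is 17% to 33%. These are minimum shares, because two weeks is a floor. They describe overlap only and say nothing about the size of any effect on adherence.

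**Step 3. Does anything separate the two parts?** SAP section 4.1 says secondary outcomes are compared by the methods used earlier in the SAP, and section 4.4 item 9 only names the measure. Neither divides pregnancy treatment from the postpartum goal or supply, and no limitation is stated. The protocol does list postpartum recommendations as a question of their own in aim 1.3b b: "To assess the impact of postpartum treatment recommendations on maternal outcomes". That aim concerns maternal outcomes, so it is not a plan to separate effects on adherence. It does show that the protocol sees postpartum recommendations as distinct from treatment in pregnancy.

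**Step 4. What does the randomized comparison identify?** The arms were randomized to packages, so the difference between them estimates the effect of one package against the other. Postpartum management was not randomized separately within pregnancy treatment, so no analysis by arm alone can apportion the difference.

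**The case against.** The strongest reply has four parts.

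1. **Treatment during pregnancy is shorthand for the assigned arm.** Section 3.3 says the trial tests a policy of therapy, the SAP defines its groups by randomization, and the sentence at issue sits in a background section. An intention-to-treat report by arm would be valid. That last point stands. The shorthand reading does not rescue the wording, because the supply thresholds differ explicitly after delivery and postpartum prescribing acts directly on this outcome.

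2. **The arms may hardly differ in practice.** Section 2.6.1 describes a consensus that nonpregnant women of childbearing age be treated to below 140/90, which may be what usual practice means after birth. Section 4.5 expects most women, without distinction by arm, to be on a suitable regimen by the end of the postpartum period. This stands as a limit on size. Neither passage sets a goal for the Standard arm in the first weeks.

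3. **The instrument is not in the documents.** The follow-up form (HP07) may already ask about current use, and the dispensing log (HP04) may already record supplied drug. The documents also do not show that a lower goal changes adherence among women who are prescribed treatment, as opposed to changing who is prescribed. This stands.

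4. **The outcome is deferred** to secondary studies (section 4.7.2) and to work after the primary analysis (SAP 4.4), so a full analysis plan would not be expected. True, but the wording of the aim already fixes what will be concluded.

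A reader might go further and infer that the protocol sets two different postpartum goals, or that the supply difference lasts two weeks. The documents support neither: the Standard arm has no protocol goal, and the two-week minimum attaches to the active arm's goal and drug use, not to the supply rule. Section 4.4.1 promises supply only up to delivery or later.

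**Conclusion.** The point holds as a matter of attribution. The comparison of postpartum adherence by arm is valid for the assigned strategy as a whole, from treatment in pregnancy through early postpartum management and drug supply. It does not support the narrower statement that treatment in pregnancy was the cause.

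The overlap is at least 17% to 50% of the recall window, depending on visit timing. The size of any distortion cannot be derived. That would need adherence rates, the way the items are scored, the number of women answering and each site's usual goal, and the documents give none of these. The planned 1142 per arm was set for the primary outcome and is not a count of women with adherence data. A reader might infer that a significant adherence result would be spurious, or that the bias is large; nothing in the documents shows either, and it may be near nil where usual care already aims below 140/90.

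This is minor. It concerns a deferred secondary aim that the protocol itself lists as unrelated to the primary hypothesis. The primary outcome, alpha and sample size are not affected.

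**What to change.** - **Reword** section 2.7.2 b and aims 1.3b a and 3.2b d to refer to the effect of the assigned strategy: treatment in pregnancy together with early postpartum management and drug supply.
- **In SAP section 4.4 item 9**, analyse current antihypertensive use and adherence at the 4-12 week visit (for example, over the past 7 days) in all randomized women, alongside the since-delivery measure. Keeping all randomized women avoids restricting the comparison to those prescribed a drug, a group that the postpartum rules themselves may shape.
- **Add items to HP07** on current use, and on whether postpartum drug came from the study, only if the existing forms do not already capture them.

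The current-use measure reduces the overlap but does not remove carry-over from the early weeks, so the rewording is needed either way.

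Cost: edits to one background paragraph, two aim lists and one SAP item, and at most one or two form fields. There are no extra patients or visits. The real price is that the aim claims less.

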## 3. Study Design

CHAP is a large pragmatic trial with adaptive sample size focusing on women who will be enrolled early in pregnancy with preexisting or newly diagnosed mild CHTN. The pragmatic approach follows the seminal\_design of the Hypertension Detection and Follow-up Program which compared stepped care to referred care, because of the cost, ethics and complications of a placebo controlled trial.A pragmatic open label design has been used successfully in studies of antihypertensive therapy.

#### 3.1 Primary Research Question

Does antihypertensive therapy to a pragmatic clinic BP goal <140/90, compared with ACOG recommendations (no treatment), for mild CHTN reduce the frequency of key adverse maternal and perinatal outcomes associated with CHTN including 1) a primary composite outcome (Effectiveness) including at least one of: i) fetal or neonatal death, ii) preeclampsia with severe features; iii) placental abruption, or iv) indicated PTB <35 weeks (i.e. not due to spontaneous preterm labor or membrane rupture, and 2) SGA (birth weight <10th percentile), to assess safety.

#### 3.2a Secondary Research Aims Related to Primary Question:

- a) To better quantify the risks of severe maternal cardiovascular outcomes associated with mild CHTN during pregnancy and determine the impact of treatment.
- b) To test whether antihypertensive (compared to withholding therapy) reduces the incidence of a composite of severe neonatal morbidities including at least one of BPD, ROP, NEC, IVH grades III/IV
- c) To evaluate whether the effects of antihypertensive therapy for mild to moderate hypertension during pregnancy on the primary outcome and SGA differ by a) prior antihypertensive therapy, b) racial-ethnic group, c) pre-existing diabetes, d) gestational age at randomization; e) maternal first pregnancy BMI.

[figure not shown]
#### 3.2b Secondary Research Aims Unrelated to Primary Question:

- d) To assess whether antihypertensive treatment of mild CHTN during pregnancy (compared to withholding therapy) influences post-pregnancy adherence to recommended therapy.
- e) To assess the impact of postpartum treatment recommendations on maternal outcomes
- f) To investigate the optimal gestational age to deliver women with CHTN in order to minimize maternal and perinatal complications. We will apply survival analysis methods to the trial population.
- g) To collect and store biospecimens including maternal and cord blood for future biological and biophysical studies to understand the effects of antihypertensive therapy in pregnant women with mild CHTN.
- h) To compare outcomes by standardized pragmatic clinic BP vs. standardized automated clinic BP measures.

- i) To assess whether the effect of therapy on SGA differs by whether current national standard nomogram vs. individualized nomogram for birth weight is utilized.
- j) To plan for a long-term follow-up study to evaluate the impact of treatment of mild-moderate chronic hypertension on long-term maternal and child outcomes

#### 3.3 Design Summary

This study is a multicenter randomized controlled clinical trial of 2404 women with randomization stratified by center (Figure 2). Patients with mild CHTN (based on pragmatic clinic BP measurements <160/105) will be randomized to either treatment with a first-line antihypertensive agent recommended by ACOG (labetalol or nifedipine ER supplied by the study) or other provider preferred medication (not supplied by the study), or no anti-hypertensive treatment. Consistent with the pragmatic design to evaluate the policy of therapy and not a specific medication, rarely, women who have a strong preference for their own established medication (e.g. intolerance of other medications) will be included in the study (and will use their own supply).

For participants in the active treatment group, labetalol dose, nifedipine ER dose or other antihypertensive medication dose will be escalated as needed to achieve target BP (<140/90). Dosing frequency may be increased to tid in order to control BP or to reduce side-effects. If the maximum tolerated oral dose of the first line agent is reached and BP is not at target, 2nd line treatment (labetalol or nifedipine ER) will be initiated to achieve the target BP. After delivery, goal BP will be <140/90 for at least two weeks.

In the comparison group, treatment will not be started if BP remains <160/105; for BP ≥160/105, treatment with a first line agent (labetalol or nifedipine ER) will be initiated and maintained at the lowest dose needed to keep BP <160/105. Goal BP after delivery will follow usual practice at each site.

Analysis will be by intent to treat.

